### **11.2 Determination of Sample Size**

An estimated total of 40 subjects will enroll in this study. The sample size for this study was determined based on clinical, rather than statistical considerations. A projected sample size of 8 subjects per dosing cohort is considered to be of reasonable size to achieve the objectives of this single dose escalation trial. Other factors may contribute to the final sample size, which is dependent upon the observed safety and tolerability profile, and determines the number of subjects per dose cohort, number of replacements, as well as the number of dose escalations required to achieve the maximal proposed dose of the study drug.

### **11.3 Population Analysis**

#### **11.3.1 PK and PD Population**

The PK population will include all subjects who have at least one post-dose blood sample providing evaluable PK data.

#### **11.3.2 Safety Population**

The safety population will include all subjects who receive the investigational drug. The safety analyses population will be the primary population for evaluating treatment administration, compliance and safety in the study.

## 11.4 Statistical Analysis

### 11.4.1 PK Analysis

PK parameters will include  $T_{max}$ ,  $C_{max}$ ,  $AUC_{last}$ ,  $AUC_{\infty}$ ,  $t_{1/2}$ , CL, and  $V_z$ . The concentration-time data will be summarized by descriptive statistics (n, mean, and standard deviation, coefficient of variation, median, minimum, maximum, and geometric mean) according to dosing cohort and time of the study. PK parameters will be estimated using a non-compartmental method with WinNonlin (Pharsight Corp, Cary, North Carolina). Individual serum concentration of versus actual day will be tabulated and plotted by dose level (linear and log scales). Plots of the mean or median concentrations of OsrHSA will be presented by nominal day (linear and log scale) by dose level. If 3 cohorts complete in the study, linearity in PK parameters will be tested by fitting the model:  $\log(C_{max} \text{ or } AUC) = a + b * \log(\text{dose}) + \text{Dose}$ . Dose-proportionality will be tested using Power Model.

A population PK-based modeling approach may also be applied for PK characterization and PK covariate analyses. The steady state PK profile may be projected based on the population PK model. Population PK and PD data may be analyzed using modeling approaches and may also be pooled with data from other studies to investigate any association between investigational drug exposure and biomarkers or significant safety endpoints. Alternative dosing approach, e.g., body size-based or fixed dosing, may be evaluated using a population PK/PD approach. The results of these analyses, if performed, will be reported separately.

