Study Design:	
This is a Phase 1 randomized, double blinded, placebo-controlled, single dose escalation study to evaluate safety, tolerability, PK, and immunogenicity of OsrHSA in healthy volunteers (See study design schema).
 
After a screening period of up to 28 days, the qualified subjects will be randomized to OsrHSA or placebo (6:2). Each enrolled subject will receive one single assigned dose of OsrHSA or placebo. The investigator and subjects will be blinded to treatment assignment. During the study, subjects will be evaluated for safety and tolerability, PK/PD, and activity of OsrHSA.
 
On day 1, OsrHSA or placebo will be administered as single IV infusion at a rate lower than 2 ml/min to the subjects. Patients will be observed overnight. On Day 2, after completion of the study procedures and assessments, subjects will be discharged from the clinical research center. Seven-day dose-limiting toxicity (DLT) observational period will commence upon completion of dosing at the end of infusion (EOI). Subjects will have end-of-study (EOS) follow-up visits on Day 30 after infusion.
 
The planned doses are 20, 40, 80, 140, and 200 mg/kg, dose level(s) higher than 200mg/kg might be an option(s) based on emerging data from this study and ongoing China clinical trial (China IND#: CXSL1500135; Protocol Number: HY1001) .

Dose escalation decisions will be determined based on toxicities data as well as available all available PK data observed within 7 days after dosing.

**Study participation  
Duration:**

The screening period is up to 28 days, one treatment day, and follow-up period of 30 days

**Pharmacokinetic (PK)  
evaluations:**

Blood samples for single dose PK will be collected from all subjects to determine the albumin concentration changes, they will be taken at time points listed in [Table 1](#). The PK of OsrHSA will be analyzed using standard non-compartmental analysis (NCA) by validated software WinNonLin version 6.4 or higher (Certara, NJ, USA). PK parameters derived from NCA analysis will include, but not limit to,  $AUC_{0-\infty}$  and  $AUC_{0-t}$ ,  $C_{max}$ ,  $t_{1/2}$ , CL, and  $V_d$ . PK parameters will be listed for each subject and summarized with descriptive statistics by each dose level/cohort. PK parameters will also be presented with baseline corrected.

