13. PK samples (Serum albumin) will be collected at pre-dose, 0.5h after dose initiating, EOI, and 0.5h, 4h, 12h, 24h (Day 2), 48h (Day 3), Day 5, Day 8, Day 15, Day 22, and Day 30 post EOI. The exact/actual time to collect blood will be documented.
14. Colloid osmotic pressure will be measured within 30 min predose, every 30 min after dose initiating until EOI, EOI, every 1 hour up to 6 hours post EOI, every 2 hour after 6 hours up to 12 hours post EOI, and every 4 hours until 24 hours post EOI or discharge, 48h (D3), D5, D8, D15, D22, and D30 post EOI. Blood pressure should be measured prior to each colloid osmotic pressure sampling.
15. Blood samples for ADA and Anti-HCP antibody analyses will be collected at pre-dose, D8, D15, D22, and D30 post EOI.

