### **2.3.2 Non-clinical Pharmacokinetics**

The pharmacokinetic (PK) and toxicokinetics (TK) profiles of OsrHSA were characterized in rats and monkeys following intravenous administration, which is the intended route of administration in human. In order to distinguish exogenous OsrHSA from endogenous rat serum albumin, OsrHSA was labeled with I by Chloramine-T method before administration.

Distribution, metabolism and excretion was evaluated in the single-dose PK study in rats. OsrHSA is expected to behave like HSA, an endogenous protein, in drug transportation as well as in interactions with CYP enzymes or other drug transporters. Therefore, no pharmacokinetic drug interaction studies of OsrHSA were conducted.

HpHSA was included as a benchmark control and compared with OsrHSA side-by-side in several pharmacokinetic and toxicokinetics studies. HpHSA and OsrHSA showed similar PK and TK profile among all the studies, except HpHSA showed stronger immunogenicity in rats following repeat dose administration.

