### 4.2 Study Process

The trial will include a screening period, treatment period, and follow-up period of 30 days after administration. The screening period will be up to 28 days prior to investigational product administration. The screening process will initiate upon completion of the informed consent process. Once consent is provided by each participant, a thorough screening process will take place, including detailed medical history, physical examination, vital signs, concomitant medications, safety labs (see Table 1), 12 lead electrocardiogram, urine pregnancy test, urinalysis, serology panel (refer Table 1), assessment of inclusion and exclusion criteria. Upon completion of the screening, qualified subjects will be randomized to OsrHSA or placebo (6:2). Each enrolled subject will receive one single assigned dose of OsrHSA or placebo. The investigator and subjects will be blinded to treatment assignment. During the study, subjects will be evaluated for safety and toxicity, PK/PD, and activity of OsrHSA.

OsrHSA or placebo will be administered as single IV infusion at a rate lower than 2 ml/ min to the subjects. The actual start and stop times of the infusions, along with any interruptions in the infusion will be recorded. Subjects will have end-of-study (EOS) follow-up visits on Day 30 after infusion.

The planned doses are 20, 40, 80, 140, and 200 mg/kg (Table 2), dose level(s) higher than 200 mg/kg might be an option(s) based on emerging data from this study and ongoing China clinical trial, if that is the case, an amendment will be submitted.

The protocol for the repeat dose study will be submitted as an amendment to the IND after the single dose study has been completed and analyzed. The dose schedule of the repeat dose study will be based on results obtained from the single dose study. The safety of the dose that will be used in the repeat dose study will be established before the initiation of the repeat dose study.

Dose escalation will occur sequentially after review of safety data for each dosing cohort by the safety review committee (SRC). Dose escalation to the next dose level will proceed uninterrupted as long as no pre-defined DLT or stopping criteria are met.

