#### **4.2.2 Dose-escalation Criteria:**

Tolerability and safety of subjects in a cohort will be reviewed by the SRC which is comprised of an independent Medical Monitor, site Principal Investigator, and Sponsor Study Director. Dose escalation may be stopped at any time based upon the Sponsor or Investigator's clinical assessment or judgment. Upon completion of the DLT observational period (first week after dosing), the SRC will examine safety data through Week 1 for each dose cohort in combination with all available, previously accumulated safety data, as well as available PK data, if any, from all subjects enrolled in the study to date. All cohorts will enroll 8 subjects (safety data from at least 6 or 7 subjects would be needed for SRC meeting, in case a subject discontinues the study), if no more than 2 out of 8 subjects experiences DLT as defined in the section 4.2.1, dose will be escalated to the next dose level.

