#### **6.2.4 Treatment Allocation and Administration, Dosing Regimen**

This is a Phase 1 randomized, double blinded, placebo-controlled study. Subjects will be randomized. Both subjects and investigator will be blinded.

[figure not shown]
1. Parenteral drug products should be prepared by using appropriate aseptic technique, and inspected visually for particulate matter and discoloration prior to administration, whenever solution and container permit.

2. Treatment Allocation and Administration: OsrHSA will be diluted with normal saline to a total volume of 200ml.

The total infusion time will be 2hr ± 20min.

The OsrHSA infusion rate is lower than 2ml/min. The procedures used for administration are following:

- First, set up intravenous channel and intravenous injection of 50 ml saline. The infusion rate for normal saline will be 5ml/min.
- Second, OsrHSA or placebo will be administered via an infusion line equipped with a 0.2µm in-line filter. And monitor for infusion-related AEs during administration. The rate of intravenous should be lower than 2 ml/ min and cautions should be taken. Dose interruption based on intolerability will be captured in the monitoring of infusion start and stop times.
- Third, flush with 50ml normal Saline after the dose. The infusion rate for normal saline will be 5ml/min.

All dose administrations will be performed in the clinical center under the supervision of appropriately trained staff.

Further detailed instructions on handling and administration of study drug is described in the separate Pharmacy Manual.

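### If the PK assay measures endogenous as well as infused albumin, the log-log power model in section 11.4.1 is not a valid test of dose proportionality

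*Combined protocol and SAP*

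**What the plan says.** On the analysis, section 11.4.1 fits log(Cmax or AUC) on log(dose) once three cohorts are complete and adds "Dose-proportionality will be tested using Power Model". It does not say whether corrected or uncorrected parameters enter, what happens to values that have no logarithm, or what result counts as proportional.

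On the analyte, the documents disagree:
- Table 1, note 13: "PK samples (Serum albumin) will be collected at pre-dose". The synopsis likewise describes the PK samples as measuring changes in albumin concentration, and says "PK parameters will also be presented with baseline corrected". Footnote a in section 1.3 defines baseline as the mean of two serum albumin values.
- Section 7.2 names the serum concentration of OsrHSA by a validated immunoassay, and section 11.4.1 refers to plots of OsrHSA concentrations.

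On telling the two apart, section 2.1 calls OsrHSA equivalent to plasma-derived albumin in structure and immunogenicity. Section 2.3.2 explains that a radiolabel was used in the animal work: "In order to distinguish exogenous OsrHSA from endogenous rat serum albumin". No counterpart is described for this trial.

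On design, section 4.2 states "The planned doses are 20, 40, 80, 140, and 200 mg/kg", with 6 active and 2 placebo subjects per cohort (Table 2). PK blood is drawn from all subjects.

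**The concern.** A power model needs positive exposures that rise in proportion to dose apart from multiplicative error. Total serum albumin is different: a large native background with a small drug increment on top.

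Without baseline correction, the background swamps the increment and flattens the slope. With correction, the low-dose increment is about the size of sample-to-sample variation. Cmax is then largely the maximum of 12 noisy post-dose values, which inflates the low doses. Many low-dose AUCs are zero or negative, and dropping them keeps only the subjects who happen to read high. Both effects push the slope below 1 even when the drug is exactly proportional.

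The procedure can also move albumin: "OsrHSA will be diluted with normal saline to a total volume of 200ml", with 50 mL saline before and after, 50 + 200 + 50 = 300 mL in all. Placebo subjects could show how much, but dose 0 has no logarithm, so the power model cannot include them.

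PK is a secondary objective, and section 4.2 bases the repeat-dose schedule on this study's results. A spurious less-than-proportional conclusion could carry into that work.

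**Working it through.** **The plan's own figure.** "All cohorts will enroll 8 subjects" and there are 5 cohorts: 5 x 8 = 40, as in section 11.2 ("An estimated total of 40 subjects will enroll in this study"). Active subjects: 5 x 6 = 30. Placebo: 5 x 2 = 10. The plan gives no error rate, interval level, variance or acceptance range for the proportionality test.

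**Assumptions not in the documents.** Native albumin 42-43 g/L; initial volume 42-43 mL/kg; half-lives 14-15 h and 17 d; between-subject log-SD 0.2; within-subject plus assay CV 1-5%. Non-proportional means that the 95% interval for the slope excludes 1.

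**Size of the signal.** Peak rise = dose / volume. At 20 mg/kg: 20 / 43 = 0.47 g/L. At 200 mg/kg: 200 / 43 = 4.65 g/L. Noise SD at CV 1 / 2 / 3 / 5% of 43 g/L is 0.43 / 0.86 / 1.29 / 2.15 g/L, so the lowest-dose rise is about equal to or below one SD.

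**Uncorrected values.** The noise-free slope across the 10-fold dose range is ln[(42 + 4.65) / (42 + 0.47)] / ln(10) = 0.094 / 2.303 = 0.04. Simulation gives about 0.03 for Cmax and 0.01 for AUC; the AUC slope excludes 1 in 100% of trials.

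**Corrected Cmax in undosed subjects.** The expected maximum of 12 independent standard normal values is 1.63. Multiplied by SDs of 0.42 / 0.84 / 1.26 / 2.10 g/L (1 / 2 / 3 / 5% of 42), this gives 0.7 / 1.4 / 2.1 / 3.4 g/L. A placebo subject would thus show a Cmax above the 0.47 g/L expected from 20 mg/kg.

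**Corrected values, true slope 1.** 3000 simulated trials per column, the plan's sampling times, baseline the mean of two values, 43 g/L, 42 mL/kg, steady-state to initial volume ratio 2.2:

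| Within-subject CV | 1% | 2% | 3% | 5% |
|---|---|---|---|---|
| Cmax: mean slope | 0.74 | 0.55 | 0.43 | 0.29 |
| Cmax: interval excludes 1 | 86% | 95% | 98% | 99% |
| AUC <= 0 at 20 mg/kg | 35% | 42% | 45% | 47% |
| AUC <= 0 at 200 mg/kg | 0.1% | 3% | 10% | 22% |
| Mean number lost of 30 active | 3.9 | 6.7 | 8.6 | 10.8 |
| AUC, non-positive dropped: mean slope | 0.78 | 0.47 | 0.31 | 0.18 |
| same: interval excludes 1 | 32% | 60% | 70% | 76% |
| AUC, negative concentrations set to 0: mean slope | 0.89 | 0.69 | 0.56 | 0.40 |
| same: interval excludes 1 | 21% | 37% | 46% | 55% |

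**Sensitivity.**
- With 42 g/L, 43 mL/kg and 14 h, the AUC slope (non-positive dropped) is 0.73 / 0.44 / 0.29 / 0.15. Its interval contains 1 in 63 / 37 / 29 / 23% of trials, so it excludes 1 in 37 / 63 / 71 / 77%. The Cmax interval contains 1 in 15 / 5 / 3 / 1%.
- With volume ratio 1.5, AUC is less affected. At CV 1 / 2 / 3% the slope is 0.90 / 0.63 / 0.45 and excludes 1 in 20 / 47 / 62%. At CV 1%, 29% of AUCs at 20 mg/kg are <= 0.
- At CV 0.5%, the AUC slope is 0.98 with 14-17% false findings; Cmax is still biased (0.87, 60%). At CV 0.1%, the AUC slope is 1.02 with 9%.
- On error-free AUC, as a drug-specific measure would approach, the power model behaves: mean slope 1.00, 4.4% false findings.

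**The alternative.** Regressing the EOI change on dose, with placebo as dose 0, recovers 1.00-1.02 of the true slope with 83-96% interval coverage across the runs. A curvature test on linear-scale AUC gives 5-8% false findings at CV 0.5-5%, with nobody dropped. Its EOI counterpart has little power: 43% falling to 11% at CV 2-5% for a true exponent of 0.6. Section 2.3.3 attributes the drug's action to increased plasma volume. If each gram retains an assumed 10-18 mL, the net rise shrinks to a first-order fraction 1 - 0.042 g/mL x 10 mL/g = 0.58, or 1 - 0.042 x 18 = 0.24; simulation gives 0.56-0.23. Placebo subtraction cannot remove this.

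**The case against.** The best defence is that section 7.2 already promises an OsrHSA immunoassay and section 11.4.1 speaks of OsrHSA concentrations. If that assay is specific, the problem goes. This stands, and it makes the point conditional. It does not settle the matter: specificity is not stated, section 2.1 stresses equivalence to plasma albumin, and the synopsis and note 13 say serum albumin.

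A reader might infer more than the documents support:
- That the plan puts corrected values into the power model. It says only that corrected parameters are also presented. Uncorrected values would do worse.
- That a proportional drug would be declared non-proportional whatever it does. That is nearly so for Cmax at CV 1% or more, but not for AUC, and section 11.4.1 gives no rule by which anything is declared.
- That this is the only planned test and placebo PK data go unused. Section 11.1 plans group comparisons of endpoints, and change in serum albumin is an exploratory endpoint. What is missing is placebo adjustment in the dose-exposure analysis.

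The variability, baseline and volume are assumptions, which is why ranges are shown. The objection that the linear model is weak against curvature is correct and limits what it may claim; the bias in the log-log slope remains. Finally, escalation rests on safety criteria with PK only reviewed alongside, so this does not threaten the primary objective.

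**Conclusion.** The concern holds conditionally. The documents conflict on the PK analyte, and if it includes endogenous albumin, the power model cannot test dose proportionality validly.

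Under the stated assumptions at CV 1-5%, a proportional drug yields a mean Cmax slope of about 0.75-0.3, with 1 inside the 95% interval in about 15% of trials or fewer. The mean AUC slope is about 0.8-0.15 and about 35-47% of 20 mg/kg AUCs cannot be logged; a smaller distribution volume at CV 1% softens these to 0.90 and 29%. A false less-than-proportional AUC finding occurs in roughly 20-77% of trials when non-positive AUCs are dropped and an interval-excludes-1 rule is used. The AUC bias largely disappears at CV 0.5% or below, though the false-finding rate there is still 9-17%.

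The direction of the bias is firm for CV of about 1% or more; its size depends on figures the sponsor must supply. For a secondary PK analysis this should be fixed before the PK data are analysed. It is not a defect that must hold up the trial.

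**What to change.** 1. Reconcile the synopsis and Table 1 note 13 with sections 7.2 and 11.4.1 on the analyte, and state whether the assay is specific for OsrHSA against native albumin. Keep the power model only if specificity is shown.
2. Otherwise, in section 11.4.1, make the dose-exposure analysis an arithmetic-scale regression on dose. The outcomes are the placebo-adjusted change from baseline at EOI (a fixed time, not the maximum) and an AUC over a fixed horizon. Include the 10 placebo subjects as dose 0, keep non-positive values, and use robust standard errors.
3. Report slope and curvature estimates with confidence intervals. Do not read a non-significant quadratic term as proof of proportionality.
4. State that the result describes net serum albumin change, including any drug-induced plasma-volume expansion.

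The cost is SAP wording and a little analysis. Placebo sampling error enters the correction, an arithmetic slope is less familiar than the power-model exponent, and power to detect curvature is low. No new samples are needed.

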### 11.4.2 Safety Analysis

Safety data will be summarized by treatment group using descriptive statistics. No formal inferential analyses are planned for safety comparisons. Continuous safety data will be summarized as sample size, mean, SD, minimum, and maximum, by scheduled time point and treatment for observed values and change from baseline values (as appropriate). Tabulations of frequencies and proportions, as appropriate will be used for the evaluation of categorical (qualitative) safety data.

Adverse events will be classified by SOC and term using the Medical Dictionary of Regulatory Activities (MedDRA) coding dictionary. Incidence of treatment-emergent adverse events (TEAEs) will be summarized by SOC and preferred term for each treatment group. Incidence of TEAEs will also be summarized by severity and association with the study treatments.

Concomitant medications will be presented in summary tables and listings.

All safety data summaries will be based on the Safety Analysis Set. No statistical tests will be performed for the safety endpoints.

Missing data will be treated as they are. No imputations of missing data are planned.

### **11.4.3 Immunogenicity Analysis**

All samples will first be analyzed for ADAs in a screening assay. Study samples with results below the screening cut-off will be reported as negative for ADAs. In the event of a positive result in the screening assay, samples will be analyzed in the confirmatory assay.

The incidence of ADA will be summarized for all subjects who received at least one administration of study drug. Impact of ADAs on PK, PD, and safety of the study drug will be evaluated, if applicable.

### **11.5 Tabulation of Individual Participation Data**

Data tabulations will summarize the following numbers of subjects:

- Enrolled
- Study drug treatment dose received
- Evaluable for safety
- Protocol violations
- Protocol completions
- Withdraw from study due to:
  - Adverse event
  - Physician's recommendation
  - Withdrew consent
  - Lost to Follow-up
  - Other reasons as collected on the eCRF

